A key issue in many settings, including ours, is that testing falls into a separate budget from the treatment of patients with CDI infections. This has the potential to distort the decision of whether to run a test and, if so, what sort of test. The distortions are of two types. First, the hospital may decide to order more tests than is optimal, since the tests are perceived as "free" from the perspective of decision-makers. At the same time, the diagnostic facility may choose low-cost, slow diagnostics, because the costs associated with delays in test results are borne by the hospital. This is a classic case of silos in health care costs inefficiently distorting policy decisions, with potentially negative results for both patient health and costs.

Many institutions follow the clinical practice guidelines provided by the Infectious Diseases Society of America for the management of *C. difficile* (Cohen et al., 2010). As part of routine Infection Prevention and Control (IPC) management, patients with acute diarrhea of unknown cause are pre-emptively placed in private rooms with additional contact precautions, which mandate the use of gowns and gloves for healthcare workers. This is also known as patient isolation. Investigation for gastrointestinal pathogens is typically initiated and the duration of patient isolation depends largely on the result of microbiological testing. When severe or complicated CDI is suspected, patients are initiated on empiric treatment as soon as the diagnosis is suspected. Generally, oral metronidazole is used for mild-to-moderate CDI and oral vancomycin for severe CDI. Among hospitalized patients with acute diarrhea, initiation of pre-emptive management for CDI is common. With requested CDI screening, 85% are negative on GDG screen and 89% are negative post PCR confirmation.

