This study is a cross-sectional CRXO in that, each cluster-period consists of different individuals (patients). The order in which the interventions are delivered to each cluster (ward) is randomized to control for potential period effects. Within Foothills Hospital there are 40 wards which will be observed over a 12-month period. Each ward is randomly assigned to administer one of the two interventions for the first 6-month period (Period 1). In the second 6-month period (Period 2), the ward will administer the other intervention. Within each ward (cluster) there are two cluster-periods. Study outcomes during Period 1 and Period 2 intervention will be compared in both arms (NPT and centralized laboratory testing).

NPT testing can deliver results within several hours, while typically off-site testing takes one to two days. If NPT and the off-site testing deliver identical test results as our pilot data suggest, we can follow the clinical outcomes for each arm without the confounder of differences in test performance. As a contingency, if variation in test performance characteristics is found, analysis of patient outcomes will take this into consideration.

For patients without CDI, the antibiotics, and in many cases, the isolation, are unnecessary. NPT testing has the potential to avoid this unnecessary use of antibiotics and to avoid costly isolation procedures for the day+ that standard testing requires. It also enables a better-directed diagnostic process for the cause of diarrhea. For patients who are positive for CDI, the earlier test result will influence downstream events such as initiation of antibiotic therapy, resolution of disease, hospitalization days, and other clinical outcomes.

We hypothesize that NPT for CDI will result in reduced patient isolation days in the hospital, decreased morbidity and mortality, reduced unnecessary antibiotic use and overall reduced costs to the health care system, including both hospital and laboratory.

Previous data has indicated that the mean number of patients a ward is 39/month ($SD=43$) for a total of 1578 patients in a 6-month period and the mean number of negative patients is 33/month ($SD=34$) for a total of 1300 negative pts in a 6-month period. The inclusion criteria will be diarrhea in adult patients admitted to four acute care hospitals in the Calgary region being tested for CDI. Outpatients and patients in the emergency room will be excluded.

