We will also account for the severity of CDI. The epidemiological definition for severe CDI is that primarily proposed by Cohen *et al*. This definition has been used by infectious disease specialists in Alberta to guide the management and treatment of patients with CDI. Patients with severe CDI will have leukocytosis with a white blood cell (WBC) count $>15,000$ cells/ μ L OR an elevated serum creatinine (i.e. 200 μ mol/L or greater). The inpatient laboratory results that will be considered to meet the definition for severe CDI will be those collected within a 7-day infection window around the date the laboratory tested positive for *C. difficile*. The presence of either measure meeting the criteria within the defined infection window will qualify as meeting the definition of severe CDI. If either criterion is measured more than once during the infection window, the highest value will be used to represent the severity of CDI. The laboratory values will be provided by Calgary Laboratory Services and linked to the positive *C. difficile* test results. In-hospital, all-cause mortality will be defined as death occurring during the acute care encounter where specimens were collected for *C. difficile* testing.

We predict that, given the large number of patients and randomized study design, matching of patients by age, gender, and co-morbidities is not required. Potential hurdles in the study model are logistical challenges associated with building a testing and reporting system for a hospital on a 24hrs/7 days per week basis. The strength of the proposal lies in the scale and nature of the study which seeks to establish the medical and economic benefit of NPT versus centralized testing. The results could dramatically influence public health policy in this country and seek to bridge traditional silos, namely the laboratory and hospital budgets. Data on costs will be furnished by our partners at Calgary Laboratory Services and Alberta Health Services (Infection Prevention and Control).

Data Analysis:

In order to make the data generalizable to other settings, an appropriate econometric methodology to assess the impact of the impact of the NPT testing through multivariate regression is required. For example, consider the following potential model:

$$y_i = \beta_0 + \beta_1 POCT_i + \beta_2 Z_i + \beta_3 H_i + \beta_4 T_i + u_i$$

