where y_i is the outcome variable of interest (such as the hours that a patient spends in isolation or the days of hospitalization); $POCT_i$ is a dummy variable indicating whether the patient had a NPT test; Z_i is a vector of individual-specific variables, including age, gender, CDI status and severity, and the like; H_i is a set of dummies indicating ward; T_i is a set of dummies indicating season or month; and u_i is an individual-specific error term. This approach allows us to identify the effect of NPT testing independent of patient, ward and season. In addition, the NPTT dummy can be interacted with other variables to see whether the impact of NPT testing is higher for certain types of patients

Beyond evaluating the relative merits of NPT versus centralized testing, studies will also look at the microbiology of CDI in this study. Specifically, we will conduct several laboratory methods to examine antibiotic resistance and genetic variation in CDI. For example, whole genome sequencing of cultured CDI isolates may inform us about the transmission of specific strains in our setting. Indeed, certain strains and states of gut dysbiosis may result in increased morbidity and mortality (Shahinas et al., 2012). We will look at the microbiome of patients in this study to determine if dysbiosis contributes to adverse clinical outcomes. We will also correlate the strain types with the results of testing to determine if genetic variation affects test performance. Cultured toxin-producing CDI isolates will serve as a gold standard to evaluate test performance.

Originality of the proposal:

It is our view that in the clinical laboratory arena NPT for CDI (described earlier) as a technology has already matured to a stage that translation of this technology into the clinical domain is now needed. As described previously, several formats including lateral flow are currently available through major diagnostic companies. The Infectious Diseases Society of America (IDSA) has recently recommended that rapid diagnostic testing can enhance antimicrobial stewardship by promoting appropriate antibiotic use for respiratory infections (Barlam et al., 2016). However, the recommendation is listed as “weak” with “low-quality evidence”.

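### The example regression codes treatment by the test the patient had; coding by the ward's randomised allocation is not stated (minor, cheap to settle)

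*Combined protocol and SAP*

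**What the plan says.** Under Study Objectives, wards at one hospital are randomised to the order of near-patient testing (NPT) and centralised testing, with one intervention in each six-month period. The same section says "Study outcomes during Period 1 and Period 2 intervention will be compared in both arms", naming the arms as NPT and centralised testing. It does not say what places a patient in an arm.

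Under Data Analysis the model is introduced with "For example, consider the following potential model". It regresses the outcome on POCT_i, individual covariates Z_i, ward dummies H_i and season or month dummies T_i. POCT_i "is a dummy variable indicating whether the patient had a NPT test", and Z_i "is a vector of individual-specific variables, including age, gender, CDI status and severity, and the like". Hours in isolation is one of the example outcomes, and the primary endpoint is duration of contact precautions.

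The document does not mention intention-to-treat, coding by allocation, or how to classify a patient whose specimen is tested by the other route.

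**The concern.** In a cluster crossover trial, randomisation protects the comparison between ward-periods as allocated. The test a patient actually received is an event after allocation. If specimens are sometimes tested off allocation, and the patients concerned tend to have longer or shorter isolation, coding by test received moves a selected group from one side of the comparison to the other. The coefficient on POCT_i then mixes the effect of NPT with that selection, and the test on the primary endpoint can lose its nominal error rate.

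The plan reports no departures. It does name, under Methods, the logistics of running testing and reporting around the clock as a hurdle. If that hurdle led to NPT-ward specimens being sent to the central laboratory, departures would run in one direction, which is the case where bias can arise. The plan does not say that this will happen, or that such patients would differ.

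**Working it through.** The plan has no figure of its own to reproduce here. The check is an illustration of what turns on the coding.

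Inputs from the plan:
- 40 wards and two periods (Study Objectives).
- About 3,000 patients (Originality of the proposal), hence about 1,500 allocated to NPT.
- "89% are negative post PCR confirmation" (Background), so about 11% are CDI positive.
- The expected gain: NPT is said to have the potential "to avoid costly isolation procedures for the day+ that standard testing requires". One day is used as the yardstick.

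Assumptions, none of them in the plan:
- f, the share of NPT-allocated patients tested centrally. At 2%, 5% and 10% of 1,500 this is 30, 75 and 150 patients.
- D, the days by which such patients' isolation differs from others' after adjustment for Z_i.
- SD of isolation days: 5, with 3 and 7 as a range.
- No correlation within ward-periods beyond the ward and period terms.

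**Bias.** Let A be allocation (half the patients in each arm), C ~ Bernoulli(f) mark patients who would be diverted, and R = A(1−C) be the test received. Departures occur only from NPT wards and there is no true effect. After removing ward and period:

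- Cov(R, Y) = −D·f(1−f)/2
- Var(R) = (1−f)/2 − (1−f)²/4 = (1−f²)/4
- bias = Cov/Var = −2fD/(1+f)

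At D = 1: −0.04/1.02 = −0.04 day at f = 2%; −0.10/1.05 = −0.10 at 5%; −0.20/1.10 = −0.18 at 10%. The last two are about 10% and 18% of one day. D = 0.5 halves these values, and D = −1 reverses their sign.

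**Rejection of a true null.** SE = 2·SD/√3000/√(1−f²). The rejection rate is Φ(−1.96 + |bias|/SE) + Φ(−1.96 − |bias|/SE). At SD 5 the SE is about 0.18.

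| f | D | SD | Rejection, received-test coding |
|---|---|---|---|
| 2% | 1 | 5 | 5.5% |
| 5% | 1 | 5 | 8.2% |
| 10% | 1 | 5 | 16.8% |
| 10% | 0.5 | 5 | 8% |
| 10% | 1 | 3 | 37.9% |
| 10% | 1 | 7 | 10.9% |

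With D up to 1 and f up to 5%, the bias is below the SE for every SD from 3 to 7.

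**Simulation at trial size** (n = 3,000, 40 ward dummies plus period, SD 5, 3,000 runs; mean estimate in days and rejection rate under no effect):

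| Scenario | Received-test coding | Allocation coding |
|---|---|---|
| f = 0 | −0.001, 4.7% | same |
| f = 2%, D = 1 | −0.037, 5.1% | 0.002, 4.8% |
| f = 5%, D = 1 | −0.088, 7.3% | 0.008, 5.0% |
| f = 10%, D = 1 | −0.178, 16.3% | 0.003, 5.2% |
| f = 10%, D = 0.5 | −0.090, 7.5% | 0.001, 5.1% |
| f = 10%, D = 0 | 0.001, 5.0% | 0.001, 5.5% |
| f = 10%, D = −1 | 0.181, 15.7% | −0.001, 5.3% |
| 10% crossing both ways, D = 1 | −0.006, 4.7% | −0.004, 4.6% |

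**What Z_i removes.** Suppose f = 10%, 30% of diverted patients are CDI positive against 11% overall, and CDI adds 5 isolation days (the 30% and the 5 days are assumed). Positivity in the others is then (0.11 − 0.10×0.30)/0.90 = 8.9%. The unadjusted difference is 5×(0.30 − 0.089) = 1.06 days, and the bias is −0.182×1.06 = −0.19 day. With CDI status in the model, the simulated bias falls to −0.005. If a further 0.5 or 1 day remains that Z_i does not capture, the bias is −0.09 or −0.17.

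**With a true effect of −1 day in those tested by NPT:**

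| f | Allocation coding, −(1−f) | Received-test, D = 0 | Received-test, D = 1 |
|---|---|---|---|
| 5% | −0.95 | −1.00 | −1.10 |
| 10% | −0.90 | −1.00 | −1.18 |

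**The case against.** The natural reading of the design already gives allocation coding: a ward administers one intervention per period, outcomes are compared by arm, and no passage has a patient or clinician choosing the route. On that reading, the wording of POCT_i is shorthand for being tested in an NPT ward-period, inside an equation offered only as an example. This is plausible, and it is why the point is not put as a contradiction. But the equation is the plan's only operational definition of the treatment variable, and an analyst following it literally would code by test received.

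The sizes are assumed, and D = 1 day after adjustment may be generous. Z_i includes CDI status, and the Background says "the duration of patient isolation depends largely on the result of microbiological testing", so adjustment could remove much of any difference. This stands: only what remains after Z_i matters.

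The rejection rates also ignore ward-period correlation. With an assumed correlation of 0.02 and 3000/80 = 37.5 patients per cluster-period, the variance rises by 1 + 36.5×0.02 = 1.73. If the inference allows for this, the D = 1, SD 5 rates fall from 16.8% to about 11.7% at f = 10%, and from 8.2% to about 6.8% at f = 5%. This also stands. The bias itself does not change.

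Finally, a sentence about the ward and period of collection does not by itself settle repeat specimens or patients tested during wash-in or wash-out. That is fair. The first can be covered in the same sentence; the second is a separate gap.

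**Conclusion.** The concern holds as a minor point. The plan randomises ward-periods, words its only treatment variable by test received, and never states that patients are classified by allocation. No error is shown: with full adherence the codings are identical, and the bias is zero if departures are symmetric or unrelated to outcome. Under one-sided departures and a residual difference of one day, the bias is −0.04 to −0.18 day for f between 2% and 10%. It is negligible against the SE at 2% and material to the error rate at 10%. These figures depend on assumed f, D and SD and are not a forecast for this trial. Under no true effect, allocation coding stayed within about 0.01 day of zero and close to 5% rejection in every scenario simulated.

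**What to change.** State that, in the primary analysis, POCT_i is the intervention randomised to the ward where the patient's first eligible specimen was collected, in the period of collection, whichever test was run. Use the same ward for H_i. Report the share of specimens tested off allocation in each arm, and keep received-test coding as a secondary analysis. Say separately how patients tested in wash-in or wash-out are handled.

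The coding rule costs one sentence and one line of reporting, with no change to design or sample size. The statistical price is dilution if adherence is poor: a true −1 day effect becomes −0.98, −0.95 or −0.90 at f = 2%, 5% or 10%. With full adherence no result changes.

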The intervention of interest is implementing a new RDT to Near Patient Testing (NPT); screening for CDI to be performed at the hospital rapid response laboratory (RRL) instead of the DSC. Techlab Inc. offers a lateral flow assay (C. DIFF QUIK CHEK COMPLETE® test) that detects both GDH and Toxin simultaneously and further simplifies the testing algorithm. As prescribed in the two-step algorithm, GDH and Toxin negatives will be reported out immediately as negative for CDI, while positive or discrepant results will be confirmed at the DSC using NAAT. The vast majority of requests for CDI testing are negative thus allowing a majority of results to be reported immediately to patient wards without NAAT confirmation at the DSC.

Study Objectives:

Calgary presents a unique opportunity to examine the effect of decentralizing CDI testing to Near Patient Testing. While it is not possible to perfectly duplicate the testing technology (described earlier) at NPT and the central laboratory, it is possible to provide equivalent testing. In a pilot study, we tested 20 stool samples by our current CLS centralized testing algorithm and anticipated NPT algorithm. Both algorithms rely on a two-step approach, namely GDH screen and molecular confirmation for toxin although the platforms are different. We had 100% concordance in the final result (presence of toxin) between the two algorithms. Further confirmation of this assumption (equivalence in performance) will be completed with a larger sample size prior to finalization of the NPT algorithm.

We will conduct a two-period, two-intervention, cluster randomized crossover (CRXO) design study at Foothills Hospital. Each cluster (ward) will receive each of the two interventions in a separate 6-month period of time leading to two “cluster-periods” with associated “wash-in” and “wash-out” periods attached. The interventions are RDT using NPT for CDI, and testing for CDI using centralized testing at the DSC.

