Our primary endpoint is to examine the differential effect of NPT on the duration of contact precautions (i.e. patient isolation days). Secondary outcomes will compare turn-around times from specimen submission to result, days of hospitalization, the number of days of antibiotic therapy, the incidence of CDI, severe CDI, and in-hospital mortality. A comprehensive economic evaluation will be performed to determine the cost of testing, patient isolation, and hospitalization for all patients in the control and treatment arms.

Methods:

Contact precautions (i.e. patient isolation) due to CDI will be defined as an order by healthcare workers for contact precautions within the 7-day infection window of a CDI diagnosis. The length of time on contact precautions will be defined as the calendar date contact precautions are completed or patient discharge date minus the calendar date contact precautions are ordered. Data on contact precautions will be extracted from the clinical patient management system in Calgary, known as Sunrise Clinical Manager (SCM). It is used extensively in all Calgary acute care facilities and emergency departments. These data include patient identifiers (e.g. patient health number, names, date of birth), start and stop dates of isolation, facility, and patient care unit where isolation order was placed, and reason for isolation (e.g. CDI, diarrhea). These data will be linked to the specimen results tested for CDI by the patient's Personal Health Number (PHN). Turn-around times from specimen submission to result will be provided by Calgary Laboratory Services. Days of hospitalization will be defined as the difference between the admission and discharge date. The specimen results will be linked to the Discharge Abstract Database using the patient's PHN to determine during which acute care encounter the specimen was collected and the admission/discharge dates of that encounter. Antibiotic therapy will be defined as the administration of antibiotics initiated on the day of and up to 48 hours after specimen collection for CDI testing. Total days of antibiotic therapy during the acute care encounter will be defined as the calendar date antibiotic therapy is completed minus the calendar date antibiotic therapy is ordered. The data will be extracted from SCM.

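### The only regression model, offered as an example, adjusts for CDI severity, which can include values after the randomised test result, so β₁ need not be the total effect of NPT

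*Combined protocol and SAP*

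**What the plan says.** Data Analysis introduces its regression with "For example, consider the following potential model". The model contains an NPT indicator with coefficient β₁, ward dummies, season or month dummies, and patient covariates: "Z_i is a vector of individual-specific variables, including age, gender, CDI status and severity, and the like". No other model is given, and no rule limits covariates to those measured before the test.

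Methods holds the only severity definition. A patient is severe if white-cell count or creatinine passes a threshold in samples "collected within a 7-day infection window around the date the laboratory tested positive". With repeated measurements, "the highest value will be used to represent the severity of CDI". The split of the window before and after that date is not stated.

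The secondary outcomes at the end of Study Objectives include "the incidence of CDI, severe CDI, and in-hospital mortality". Earlier in that section, the expectation for CDI-positive patients is that "the earlier test result will influence downstream events such as initiation of antibiotic therapy, resolution of disease, hospitalization days, and other clinical outcomes".

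**The concern.** Taken together, these statements put a variable that NPT may change on the right-hand side of the model meant to measure NPT's effect. If an earlier result leads to earlier treatment, and so to a lower peak white-cell count or creatinine, some patients who would have been classed as severe will not be. Holding severity fixed then removes that part of the benefit from β₁. An unmeasured trait such as frailty, which raises both severity and isolation time, can distort β₁ further once severity is conditioned on. For the severe-CDI outcome the model cannot be used as written, because the same variable would be both outcome and covariate.

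At stake is whether β₁ answers the policy question of what moving the test to the hospital does overall. The question is sharpest for length of stay, and for any estimate or interaction in CDI-positive patients, since only they can have a severity value.

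**Working it through.** There is no plan figure to reproduce: the documents give no outcome SD, effect size, power or rate of severe CDI.

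**Inputs from the documents**
- Enrolment of about 3000 (Originality of the proposal).
- CDI-positive share: 11%, from 89% negative after PCR (Background and Significance); or 1 − 1300/1578 = 17.6% from the planning counts (Study Objectives).
- Positives: 3000 × 0.11 = 330; 3000 × 0.176 = 528.

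**Assumed inputs (not in the documents)**
- NPT lowers severe CDI among positives by 0–10 percentage points.
- A severe case adds 3–5 days.
- Outcome SD is 5–8 days.

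**Can the covariate follow the result?** Yes, on the only definition given. If the window were centred (an assumption), 3 of its 7 days would fall after the positive-test date, and the highest value counts whenever it occurs.

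**Effect removed from β₁**

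In positives, loss = fall in severe CDI × extra days. Over all tested patients, multiply by the positive share.

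| Fall × extra days | Positives | All, 11% | All, 17.6% |
|---|---|---|---|
| 0 × 5 | 0 | 0 | 0 |
| 0.05 × 3 | 0.15 day | 0.0165 | 0.026 |
| 0.10 × 5 | 0.50 day | 0.055 | 0.088 |

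**Against the standard error (SE) of β₁**

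With equal arms and clustering ignored, SE = 2 × SD/√n.
- All patients: 2 × 5/√3000 = 0.183 to 2 × 8/√3000 = 0.292 day. For a 5–10 point fall the ratio runs from 0.0165/0.292 = 0.06 to 0.088/0.183 = 0.48.
- Positives: 2 × 5/√528 = 0.435 to 2 × 8/√330 = 0.881 day. The ratio runs from 0.15/0.881 = 0.17 to 0.50/0.435 = 1.15. The upper figure combines the largest fall, most extra days, smallest SD and highest positive share.
- Positives, mid-range: 7.5 points × 4 days = 0.30 day; n = (330 + 528)/2 = 429; SE = 2 × 6.5/√429 = 0.63; ratio 0.48.

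**Simulation check**

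This used 3000 patients, 40 wards, two periods and 400 runs. It assumed 35% severe among control positives, 4 extra days for positives, SD 6 and an effect of −1 day in negatives; CDI status stayed in the model.
- No change in severity: adding severity moved β₁ by 0.001 day or less in size.
- 5 points, 3 days, 11% positive: 0.015 day overall, 0.139 in positives.
- 10 points, 5 days, 17.6% positive: 0.084 day overall (SE 0.223, ratio 0.38) and 0.492 in positives (SE 0.583, ratio 0.84).

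**Sensitivity**

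The bounds are only as wide as the inputs. A 15-point fall (50% severe, cut by 30%) with 5 extra days gives 0.15 × 5 = 0.75 day in positives and 0.132 day over all patients at 17.6%; the latter is 0.132/0.292 = 0.45 to 0.132/0.183 = 0.72 SE. A separate simulation of that case with an unmeasured frailty variable raised the all-patient shift from 0.134 to 0.152 day, in the same direction.

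**The case against.** **The model is an illustration.** This stands, and it lowers the stakes: a reader might infer that the committed primary analysis is biased, and the documents do not support that. But no other model is given, and fitting this one as written would carry the fault.

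**The covariate's timing is unspecified.** Nothing says that severity in the model uses the Methods definition. That is true, but it is the only definition available and it admits post-result values.

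**A commitment to adjust elsewhere.** A reader might take "We will also account for the severity of CDI" in Methods as a second commitment to covariate adjustment. It sits among the outcome definitions, between antibiotic days and mortality, and reads more naturally as introducing the severe-CDI outcome. It needs no rewording.

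**The path is narrow.** This stands in part. Background and Significance says suspected severe or complicated cases are treated before any result, and that in the NPT arm "positive or discrepant results will be confirmed at the DSC using NAAT". A patient already over a threshold before the result is severe in either arm. These points shrink the path without closing it, since Study Objectives still predicts an effect in positives. No passage supports any particular fall in severe CDI, and zero is possible.

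**The size can be overstated.** A reader might infer a typical loss of a full standard error. The 1.15 figure is a corner of the assumed ranges. Nothing was calculated for mortality, and the length-of-stay argument rests on the same generic SD.

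**The size can also be understated.** A reader might conclude that the primary estimate is safe. That assumes all tested patients are analysed. Methods ties CDI contact precautions to a window around a CDI diagnosis; read literally, that could confine the primary endpoint to positives.

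**Conclusion.** The point holds as a fault in the example model, with its size unknown from the documents. A severity-adjusted β₁ need not be the total effect of NPT, and the model cannot serve unchanged for the severe-CDI outcome.

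On assumed falls in severe CDI of up to 10 points, the shift is zero to under half a standard error if all tested patients are analysed. In CDI-positive patients a 5–10 point fall gives roughly 0.2–0.8 standard errors, about 0.5 at mid-range, with clustering ignored in the formula; it is zero if NPT does not change severity. Which range applies to isolation days depends on how the contact-precautions definition is read. On these inputs the shift is toward no effect, so it would hide a benefit rather than create one. The change should be made, with medium confidence in its practical importance.

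**What to change.** In Data Analysis, take severity as defined in Methods out of the patient covariates in the main model for every outcome. Use only covariates fixed at or before specimen collection (age, gender and, if wanted, pre-specimen white-cell count or creatinine), with the ward and time terms. Report any model adjusted for the Methods severity variable as a labelled supportive analysis. Keep the Methods definition for the severe-CDI outcome.

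CDI status is a separate matter. It may stay as a covariate for isolation and hospital days if the larger equivalence check promised in Study Objectives holds; otherwise the contingency stated there applies.

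The cost is wording and a small loss of precision, with no new data. With CDI status kept, dropping severity raises the SE by √(1 + p·s(1−s)·d²/SD²) − 1, where p is the positive share, s the severe share of positives (assumed 20–50%) and d the extra days.
- All patients: 0.12% (p = 0.11, s = 0.20, d = 3, SD = 8) to 2.18% (p = 0.176, s = 0.50, d = 5, SD = 5).
- Positives only (p = 1): 1.12% to 11.8%.

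Pre-specimen laboratory values may recover some of this.

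### The only analysis model has no Period 1 versus Period 2 term and lets season dummies be the sole time adjustment; if a season straddles the crossover, the period effect is not fully removed

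*Combined protocol and SAP*

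**What the plan says.** Study Objectives describes a two-period cluster crossover in which each ward "will receive each of the two interventions in a separate 6-month period of time". The setting is one hospital: "Within Foothills Hospital there are 40 wards which will be observed over a 12-month period". Wash-in and wash-out periods are attached to the cluster-periods, but neither their length nor their handling in the analysis is stated. No start date is given.

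The same section recognises period effects and relies on randomisation to deal with them: "The order in which the interventions are delivered to each cluster (ward) is randomized to control for potential period effects". It also gives historical ward sizes: "the mean number of patients a ward is 39/month", with an SD of 43 and a total of 1578 patients in 6 months.

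Data Analysis introduces its regression with the words "For example, consider the following potential model". The model has an NPT dummy, patient covariates, a ward term ("H_i is a set of dummies indicating ward") and a time term ("T_i is a set of dummies indicating season or month"). The stated benefit is: "This approach allows us to identify the effect of NPT testing independent of patient, ward and season". Period is not among the things listed, and no other model for the clinical outcomes appears in the documents.

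**The concern.** In a two-period crossover, each ward's NPT effect is a difference between its two periods. Anything that changes the outcome between the periods (isolation policy, an outbreak, staff experience) enters that difference, with opposite sign in the two sequences. It cancels if the sequences carry equal patient weight or if the model contains the period contrast.

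Neither is guaranteed here. The ward-size SD exceeds the mean, so a few large wards can dominate and one random allocation may carry unequal weight in the two orders. Season dummies contain the period contrast only when every season lies wholly within one period. If a season spans the crossover in a 12-month study, another season pools the first and last months of the study, and part of the period difference is left unadjusted. What is at stake is extra error in the NPT coefficient that a standard error built on an individual-level error term would not reflect.

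**Working it through.** **1. Ward sizes.** The plan labels 39 as monthly. As a 6-month count per ward, 39 × 40 = 1560, within about 1% of the stated 1578. As a monthly count, 39 × 40 × 6 = 9360, which does not fit. For test-negative patients, 33 × 40 = 1320 against the stated 1300. I therefore read both means and their SDs as per-ward counts over 6 months. The coefficient of variation (CV) is 43/39 = 1.10 for all tested patients and 34/33 = 1.03 for negatives.

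**2. When a season straddles the crossover.** Assume three-month seasons (December–February and so on) and a crossover on the first of a month. Starts in March, June, September and December nest seasons within periods. The other 8 start months do not. If the first month of each period is excluded as wash-in, starts in February, May, August and November also become nested, which leaves 4 of 12.

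**3. Share of the period contrast left by season dummies.** Code period as −½ or +½ and assume each ward's monthly rate is constant. The total sum of squares over 12 months is 12 × ¼ = 3. With a January start, December–February holds two Period 1 months and one Period 2 month, and June–August holds one and two. Each contributes 3 × (2/3)(1/3) = 2/3; the other two seasons contribute 0. The share left is f = (4/3)/3 = 4/9. The other straddling starts give the same value.

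**4. Leakage into the NPT coefficient.** Let δ be the patient-weighted imbalance in order: patients in wards of one sequence minus patients in wards of the other, divided by all patients. With ward dummies, least squares on a pure period step of D gives an NPT coefficient of

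leak = D × f δ / [1 − δ²(1 − f)].

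With no time term f = 1 and the leak is D δ. With a period indicator, nested seasons, or month dummies and a crossover on a month boundary, f = 0 and the leak is 0. A direct weighted least-squares fit to one simulated allocation matched the formula.

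**5. Typical size of δ.** For a random 20:20 split of 40 wards, SD(δ) = CV/√40 = 1.10/6.32 = 0.174. This gives:

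- No time term: SD about 0.175 D.
- Straddling seasons: 4/9 × 0.174 = 0.077 D from the leading term. Simulation with gamma sizes gives 0.078 to 0.083 D, 95th percentile about 0.16 D.
- Period indicator: 0.

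The mean over allocations is about zero in every case.

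**6. Sensitivity, straddling seasons.**

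- Lognormal sizes: SD 0.073 D.
- CV 1.03: SD about 0.073 D.
- Independent coin-flip allocation in place of 20:20: SD 0.113 D.
- Equal wards split 20:20: 0 under every choice of time term.
- January start with the first month of each period excluded: f = 1/2.5 = 0.4, so SD about 0.4 × 0.174 = 0.07 D.
- Mid-month start and crossover with calendar-month dummies: two calendar months are half in each period, so f = 1/6 and SD about 0.03 D.

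**7. Scale against sampling error.** The documents give no D, outcome SD or intracluster correlation, so this step is illustrative. With N = 2 × 1578 = 3156 treated as independent patients, the SE is about 2/√3156 = 0.036 outcome SDs. A nominal 5% two-sided test then has an error rate, averaged over allocations, of 2Φ(−1.96/√[1 + (0.08 D/0.036)²]):

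| Assumed D (outcome SDs) | Type I error |
|---|---|
| 0.1 | about 5.6% |
| 0.2 | about 7.4% |
| 0.5 | about 19% |

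Within-ward correlation would enlarge the SE and make the leakage relatively smaller.

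**The case against.** The strongest reply is that the equation is explicitly illustrative and already lists month, which removes the period effect when the crossover falls on a month boundary. On that view the plan needs one choice made, not a correction. Much of this stands, and it is why the point is minor. It does not dispose of the point: this is the only outcome model given, one of its two permitted options can perform worse than the other, and neither is the period term that the design calls for.

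Four stronger readings are tempting, and the documents do not support them.

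- *The NPT estimate is biased.* Order is randomised by ward, so the leakage averages about zero over allocations. It is chance error in the single allocation drawn.
- *Season dummies do nothing about period.* Straddling seasons cut the leakage SD by about half, from about 0.175 D to about 0.08 D.
- *Seasons will usually straddle the crossover.* That depends on a start date, a definition of season and a wash-in rule that are not stated. Under one plausible wash-in rule only 4 of 12 start months are affected.
- *Month dummies are as good as a period indicator.* Only if the crossover falls on a month boundary.

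It is also fair to object that the stated SD of 43 may include month-to-month variation. Ward inequality, and with it the leakage, would then be smaller.

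**Conclusion.** The point holds in limited form. The model has no period term and permits season as its only time adjustment; if a season straddles the crossover, the period effect is not fully removed. The error in the NPT coefficient then has SD about 0.08 D, against 0 with a period indicator. This rests on the 6-month reading of the ward sizes, gamma-distributed sizes, a 20:20 split, three-month seasons and a crossover on a month boundary. The practical size cannot be stated because D is not given. It is small for period effects of 0.1 to 0.2 outcome SDs and matters only for much larger shifts, which nothing in the documents suggests. Minor severity.

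**What to change.** In Data Analysis, prespecify an explicit Period 1 versus Period 2 indicator alongside the ward dummies, and keep calendar-month or season dummies as an optional addition. Do not rely on month dummies alone unless the crossover is fixed to a month boundary. The plan should also state the start and crossover dates and how wash-in and wash-out time is handled in the analysis, since these decide whether any calendar term nests within period.

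The cost is one degree of freedom for the indicator, or at most 11 for a full set of month dummies, among about 3000 patients. No new data are needed, and there is no change to the design or conduct. It is a free improvement.
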